- **Emergency department or COVID-clinic patients (patient is still in the emergency department or clinic):** For the sake of healthcare provider safety, and to minimize the spread of the virus, this visit will occur via a HIPAA compliant telemedicine consultation using tablets with telemedicine capabilities housed in the emergency department or with the study team. At this visit, consents will be reviewed in detail with the subject or LAR. The subject or LAR will have the opportunity to ask questions. If the patient (or LAR) agrees to become a study participant, electronic consent will be obtained using HIPAA and rule 11 compliant

MEDICAL PROTOCOL (HRP-590)

SHORT PROTOCOL TITLE: Randomized control trial of losartan for outpatients with COVID-19

VERSION DATE:5APR2020

electronic consent, stored and maintained in a secure RedCap server (see departmental policy on eConsent, attached).

- *Non-emergency department or COVID-clinic patients (patient returned home) or drive-thru clinic patients: For the sake of healthcare provider safety, and to minimize the spread of the virus, pre-screening and consent will occur through a video connection or phone call.* At this visit, consents will be reviewed in detail with the potential participant. The potential participant will have the opportunity to ask questions. If the participant agrees to become a study participant, electronic consent will be obtained using HIPAA and rule 11 compliant electronic consent, stored and maintained in a secure RedCap server (see departmental policy on eConsent).
- Eligible patients who meet inclusion criteria but do not have a documented creatinine and blood pressure reading within 7 days of the return of their positive COVID19 test results will undergo remote consent and enrolled. However, prior to randomization they will be required to participate in additional study screening at a clinic location prepared to accept known COVID-19 positive patients. The additional screening procedures will include: a blood pressure, creatinine, and potassium.

5.3 *Administration of study drug:* Patients will be given prepared components necessary for conduct of the study, including study drug (losartan or placebo), a thermometer, a home blood pressure cuff, and oropharyngeal swabs shipped supplies via same-day courier service.

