Short Form 12 Health Survey						X						X							X		
Oropharyngeal swabs	X			X		X			X		X										
Potassium / Creatinine Check																			X		
Follow-up biospecimens (OP swab + blood draw)																		@			
Electronic medical record / death index review																			X		

*Within 72 hours of + COVID-19 test results,

**In women of child-bearing age, patients must confirm negative test with study personnel prior to beginning treatment as well as confirmation of acceptable birth control method. For those capable of having children, a pregnancy test will be delivered to patients to confirm no pregnancy prior to initiation of study drug.

#Outpatient follow-ups +/- 1 day are accepted.

@ We will attempt to obtain oropharyngeal and blood biospecimens from patients hospitalized when they would otherwise have been planned

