- ***Other clinical Outcomes that may be exempt from adverse event reporting:*** Study specific outcomes as outlined in 5.1 and 5.2 are exempt from adverse event reporting unless the investigator deems the event to be related to the study procedures (or of uncertain relationship) or if the event leads to discontinuation of study procedures. The following are examples of events that will be considered study specific clinical outcomes and will be systematically tracked through the study design. The rationale for this criteria is that adverse event reporting can be sporadic and inconsistent, so events more likely to be truly related to a study intervention are better treated by consistent tracking through the systemic design and collection of potentially related adverse events:

- Hepatic events: hepatic injury or liver dysfunction that leads to an increase from baseline in the serum level of bilirubin.
- Renal events: renal failure, renal insufficiency, or renal injury that leads to an increase from baseline in serum creatinine.
- Hematologic/coagulation events: coagulopathy, disseminated intravascular coagulation, thrombocytopenia, or thrombocytosis.
- Changes in serum sodium and potassium

- ***Scales Used to Grade Severity of Adverse Events:*** All AEs will be graded in the following manner:

- Grade 1 (Mild): Events require minimal or no treatment and do not interfere with the participant's daily activities.
- Grade 2 (Moderate): Events result in a low level of inconvenience or concern. Moderate events may cause some interference with functioning.
- Grade 3 (Severe): Events interrupt a participant's usual daily activity and may require systemic drug therapy or other treatment. Severe events are usually incapacitating.
- Grade 4 (Life-threatening): Any adverse drug experience that places the participant, in the view of the Investigator, at immediate risk of death from the reaction as it occurred (i.e., it does not include a reaction that had it occurred in a more severe form, might have caused death).
- Grade 5 (Death)

- **Scales Used Attribute Adverse Events:** The Principal Investigator will assess the relationship of all AEs to any drug or study procedure:

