- **Recording and Documentation**
 - At each contact with the subject, personnel must seek information as to discomforts or adverse experiences by specific questioning and, as appropriate, by examination. This will typically occur via phone or telemedicine due to concerns regarding infectious

contagion. Information about AEs to be recorded includes event description, time of onset, investigator assessment of severity, relationship to Study Agent(s)/Intervention(s), and time of resolution/stabilization of the event. All AEs occurring during the study period (from time of consent signing to study day 15) must be documented appropriately regardless of relationship to study products or procedures unless included on the list of clinical outcomes that may be exempt from adverse outcomes reporting as part of the study protocol and outcomes. Information on all identified AEs will be recorded within 5 days recognition, while SAEs will be reported within 24 hours in the appropriate AE module of the case report form (CRF) on Redcap.

18.3 Data Safety Monitoring: A data safety monitoring board (DSMB) has been convened and includes 4 individuals meeting the key element criteria below, and includes a biostatistician with prior clinical trials DSMB experience. The DSMB will follow the guidance as outlined in the application and the attached charter unless there is a compelling, unanticipated reason to deviate from these rules. Data regarding the primary outcome (hospitalization) will be reported to the DSMB continuously, consistent with continuous study monitoring principles. The DSMB may recommend stopping the trial early only for safety, following these guidelines:

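### Section 18.2 exempts hepatic, hematologic/coagulation and serum sodium events from AE reporting as systematically tracked, but no such tracking is scheduled for participants who are not admitted

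*Combined protocol and SAP*

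**What the plan says.** Under the 18.2 item on clinical outcomes that may be exempt, the protocol points to 5.1 and 5.2 for the study outcomes and says that these "are exempt from adverse event reporting unless the investigator deems the event to be related to the study procedures (or of uncertain relationship"), with a further exception for events that stop study procedures. The examples given "will be considered study specific clinical outcomes and will be systematically tracked through the study design". They are:

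- "Hepatic events: hepatic injury or liver dysfunction that leads to an increase from baseline in the serum level of bilirubin"
- renal events shown by a rise in creatinine
- "Hematologic/coagulation events: coagulopathy, disseminated intravascular coagulation, thrombocytopenia, or thrombocytosis"
- changes in serum sodium and potassium

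The recording rules at the end of 18.2 repeat the carve-out. AEs from consent to day 15 are documented whatever their cause, "unless included on the list of clinical outcomes that may be exempt from adverse outcomes reporting as part of the study protocol and outcomes".

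On measurement, 5.2 covers people without recent values on file: "The additional screening procedures will include: a blood pressure, creatinine, and potassium". After randomization, 5.4 asks for a day-15 blood draw that includes creatinine, and the 5.5 table of events has one safety chemistry row, "Potassium / Creatinine Check". Section 1.6 collects organ-failure scores only for participants who are admitted.

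**The concern.** The exemption is a trade: AE reporting is given up for certain events because something more consistent takes its place. For three of the listed entries the replacement does not appear in the schedule.

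A randomized comparison of harm needs events recorded the same way in both arms, without the investigator's view of causation as a filter. The acute infection may itself produce similar abnormalities, so a modest excess in one arm would show only in the counts. If events are filtered out before they are counted, a report of no excess cannot be told apart from a failure to collect.

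**Working it through.** **1. Exempt list against schedule.**

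| Exempt entry (18.2) | Value needed | Scheduled by the study |
|---|---|---|
| Hepatic | bilirubin, baseline and later | none |
| Renal | creatinine | screening if not on file; day 15 |
| Hematologic/coagulation | platelet count, clotting tests | none |
| Sodium | serum sodium | none |
| Potassium | serum potassium | screening if not on file; later check in 5.5 |

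The stated ground holds in part for creatinine and potassium. It fails for the other three entries. Because no baseline bilirubin is required, the hepatic definition often cannot be evaluated from study data.

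**2. The cross-reference.** Sections 5.1 and 5.2 are Screening and Enrollment and define no outcomes. If 3.1 and 3.2 (the endpoints) were meant, none of those endpoints is hepatic, hematologic or sodium-based either.

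**3. Other data sources.**

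- Section 1.6 takes laboratory results at presentation if recorded, and 8.3 uses AST/ALT if already in the record. Both are opportunistic.
- Section 16.2 describes an automated pull of record data that includes laboratory values, but 16.4 relies on coordinator phone calls for patients not admitted.
- Banked specimens are tested later (7.1), and missed collection is not a deviation (6.2).
- The organ-failure score applies only to admitted participants. The documents do not list its components, so I do not rely on which classes it covers.

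**4. What the other rules still catch.** I read the exception for events related to study procedures as including the study drug, which the sentence does not say.

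- Events judged related or of uncertain relationship, or that stop study procedures, remain reportable.
- Serious AEs are collected to day 15 whatever their cause.
- Elsewhere in 18.2, an abnormal laboratory result is an AE if, for example, it suggests worsening organ toxicity, needs active management, or leads to treatment or further tests.

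The last two rules overlap the exempt list, and 18.2 does not say which prevails. What is exposed is a non-serious event, found in routine outpatient care, judged unlikely or not related, that does not stop study procedures, at a site that lets the exemption override the abnormal-laboratory rule.

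**5. How many participants are in this position.** The plan gives no figure on this point. From 15.2 and 4.6: 290 per arm, 1:1 allocation, admission 15% (control) and 7% (losartan). The 264 per arm in 15.2 reproduces with a continuity correction (239 without), but nothing here depends on it.

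- Not admitted = 290 × (1 − 0.15) + 290 × (1 − 0.07) = 246.5 + 269.7 = 516.2
- Share = 516.2 / 580 = 89%
- If 15% held in both arms: 580 × 0.85 = 493
- If 7% held in both arms: 580 × 0.93 = 539.4

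**6. How many events.** The documents give no rate of hepatic, platelet, clotting or sodium abnormalities in outpatients, so the number of unrecorded events cannot be computed.

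**The case against.** The strongest reply is that 18.2 leaves several routes open: the exceptions to the exemption, serious-AE collection, the abnormal-laboratory rule, and whatever the medical record holds. The list is also headed as outcomes that may be exempt. This stands. A reader might infer that these harms are recorded nowhere, or that AE collection for them is switched off. The documents do not support that.

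A second reply is textual. The hepatic entry covers injury that raises bilirubin above baseline. Where no baseline exists, the condition cannot be shown to be met, so the event arguably falls back under general AE recording. This is fair, but it makes exempt status depend on whether someone happened to have a bilirubin on file, which is a further reason to reword.

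A third concerns relevance. Section 13.1 does not list hepatic injury or the exempt platelet and clotting events among losartan's risks; anemia is listed but is not exempt; and section 15 plans no comparison of these harms. That limits the priority. It does not dispose of the point, because 13.1 does name electrolyte abnormalities, which bears on sodium, and a randomized trial should not need to anticipate a harm in order to record it.

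Finally, 18.2 argues that AE reporting is sporadic and that structured tracking is better. That is reasonable where tracking exists. For these entries the weaker method is restricted and nothing replaces it.

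**Conclusion.** The premise of the exemption is not met for hepatic events, hematologic/coagulation events and sodium changes. In non-admitted participants, about 516 of 580 (493 to 539), the narrow class of events described in step 4 can go unrecorded, and sites can treat the same finding differently because precedence within 18.2 is unstated.

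The 516 might be taken for a count of lost events. It is only the number of people for whom no scheduled measurement would show such an event. The events affected are probably few, and sporadic routine-care findings would support only a descriptive comparison by arm. Nor does the study measure only blood pressure, creatinine and potassium: it also collects temperature, swabs, surveys and blood specimens, though none of these is a stated liver, platelet, clotting or sodium measurement.

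The conclusion assumes the planning admission rates with all 580 enrolled. It also assumes that the day-15 draw adds no unnamed safety test. The wording in 5.4 is not exhaustive, but no other safety test is named beyond the 5.5 row, and 11.4 describes the draw as renal function testing.

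**What to change.** In 18.2:

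1. Remove the hepatic, hematologic/coagulation and sodium entries from the exempt list, or limit their exemption to admitted participants for whom the relevant values are abstracted.
2. State that the serious-AE rule and the abnormal-laboratory rules prevail over the exemption.
3. Correct the reference to 5.1 and 5.2. The sponsor should confirm the intended target; 3.1 and 3.2 hold the endpoints.
4. Record events in these classes through day 15 regardless of attribution, and tabulate them by arm.

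The cost is protocol wording and a few more AE records. The AE calls already in 5.4 and 5.5 can collect them, so no test or visit is added.

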6.0 Data and Specimen Banking

6.1 Data management:

- **Storage and Access:** Data collection is the responsibility of the clinical research staff under the supervision of Drs. [name] and [name]. Study data will be recorded within a RedCAP database with study personnel being granted access to the database based on the tasks listed in the Delegation of Authority log. Only deidentified data sets with all PHI removed will be shared for data analysis. The electronic consent (eConsent) forms, which will be maintained in a University of Minnesota RedCap database with established functionality for this purpose in our group. The database is HIPAA compliant.
- **Monitoring:** A monitor from Clinical Translational Science Institute (CTSI) or designated study monitor will review 100% of electronic consent documents, study drug administration data, and SAE reporting. Additionally, a random sampling of 5% of subjects will undergo full evaluation and comparison of source documentation with data entered into the study database. The first data monitoring visit will be scheduled once 10% of the cohort has been enrolled, with repeat monitoring after 50% and 100% of enrollments. Monitors will evaluate 100% of users to ensure assigned access is consistent with training and delegation of authority logs.
- **Release/Sharing:** Data will be shared among members of the study team with appropriate access assigned in Redcap based on study role, training, and delegation of authority. Data will be made available to assigned study monitors, the data safety monitoring board, the appropriate University of Minnesota oversight authorities, the Food and Drug Administration, and other state and federal regulatory authorities as required by state and federal law.
- **Data sharing:** Requests for data following study completion for sharing will be evaluated by a steering committee that will be established and will include the principal investigators. Requests will be evaluated on a case-by-case basis. If data are shared, only deidentified data will be shared.

6.2 Biospecimen management:

- **Specimen banking:** Biologic specimens (oropharyngeal swabs) provided by patients will be transported via courier service with the capacity to transport biologic materials with due consideration of communicable

diseases. Specimens will be transported and processed by the University of Minnesota BSL-3 laboratory and frozen at -80 C until the time of analysis. Samples will be deidentified and labeled only with a patient ID number.

- ***Biospecimens and protocol deviations:*** Baseline clinical laboratory results will be required to establish inclusion and exclusion criteria, and missing data will be reported as protocol deviations. However, significant barriers exist to the collection and processing of other biospecimens due to the increased containment required, meaning that not every study site may be able to accomplish these procedures. In addition, patient self-collection will lead to missing samples. While every effort will be made to obtain these biospecimens, failure to do so will not constitute protocol deviations.
- ***Specimen sharing:*** Requests for specimen sharing during or following study completion for sharing will be evaluated by a steering committee that will be established and will include the principal investigators. Requests will be evaluated on a case-by-case basis. If specimens are shared, human genetic analysis will only proceed on those patients who opt-in to genetic testing. Genetic testing of viral genomes will be allowed to proceed on all patients.

7.0 Sharing of Results with Participants

7.1 ***Sharing of results:*** Data collected within this study will be obtained from the participants themselves and recorded on collection templates or directly into Redcap, or will be obtained from the electronic medical record and thus are already available to the patient and treatment team. Any testing of biospecimens will occur at a later time point and do have specific clinical relevance and will not be shared with the patient.

7.2 ***Sharing of genetic testing***

- ***Disclosure of results:*** There is no plan to disclose genetic results to the patients as none is yet planned.
- ***If returning results to participants:*** N/A

7.3 ***Future analysis of genotypes:*** Genetic testing, while potentially an area of future investigation as a means to determine if participants with specific genetic differences are more or less susceptible to COVID-19, is not currently planned nor funded. As such, data will not be disclosed to the participants. To the extent possible in future work, participants or families with rare variants will undergo attempts at anonymization.

8.0 Study Population

8.1 ***Inclusion Criteria***

- Positive laboratory test for COVID-19 based on local laboratory standard
- Age greater than or equal to 18 years of age
- Upper respiratory symptoms (cough, rhinorrhea) or fever (>101.5)

8.2 *Rationale for inclusion criteria:* This is a pragmatic trial looking to enroll a diverse cohort of participants so the results may be broadly applicable to a wide patient population if efficacious. We do not have sufficient data to support lack of efficacy in a specific subgroup at this time to justify their exclusion. While we currently propose to exclude children due to insufficient time at the writing of this protocol to closely scrutinize safety and dosing in that group, along with logistical challenges of having different doses, we have plans to evaluate the possibility of expanding to include that patient population as soon as logistically feasible. Patients must be symptomatic to avoid enrolling asymptomatic carriers unlikely to meet the primary outcome.

8.3 *Exclusion Criteria*

- Randomization > 72 hours of meeting inclusion criteria
- Randomization > 7 days of symptom onset
- Currently taking an angiotensin converting enzyme inhibitor (ACEi) or Angiotensin receptor blocker (ARB)
- Prior reaction or intolerance to an ARB or ACE inhibitor, including but not limited to angioedema
- Pregnant or breastfeeding women
- Women able to have children not currently taking a protocol allowed version of contraception: intrauterine device, Depo-formulation of hormonal contraception (e.g. medroxyprogesterone acetate / Depo-Provera), subcutaneous contraceptive (e.g. Nexplanon), daily oral contraceptives with verbalized commitment to taking daily throughout the study, condom use or abstinence during the study. All women of child bearing age enrolled in this fashion will be informed of the teratogenic risks.
- Patient reported history or electronic medical record history of kidney disease, defined as:
 - Any history of dialysis
 - History of chronic kidney disease stage III or IV
 - Estimated Glomerular Filtration Rate (eGFR) of < 30ml/min/1.73 m² (must be have been measured within 1 month of enrollment)
 - Other kidney disease that in the opinion of the investigator, would affect losartan clearance
- Patient reported dehydration and significantly decreased urine output in the past 72 hours
- Most recent systolic blood pressure prior to enrollment <110 mmHg
- Patient reported history or electronic medical record history of severe liver disease, defined as:
 - Cirrhosis
 - History of hepatitis B or C

- Other liver disease that in the opinion of the investigator, would affect losartan clearance
- Documented AST or ALT > 3 times the upper limit of normal within 3 months of randomization (if available in electronic medical record)
- Potassium >5.0 mmol/L (must have been measured within 1 month) of enrollment
- Concurrent treatment with aliskiren
- Inability to obtain informed consent

8.4 *Rationale for exclusion criteria:* We expect treatment results to be available within 24 hours of sample collection related to delays in transport to a central facility. Coupled with delays in patient contact, 72 hours allows sufficient time for early outpatient intervention. Every effort will be made to minimize this window, however. Most patients will be hospitalized within 9 days of first symptoms, so patients with >7 days of symptoms have limited potential for benefit. Patients already taking or with prior adverse events to either an ACE inhibitor or ARB are excluded for risk of side effects. Losartan is a class D drug. Women of child bearing age (14-40) without a history of hysterectomy must have a documented negative pregnancy test in the emergency department or clinic in the past 7 days or have had a prior history of hysterectomy. Alternatively, if interested in the study, women of childbearing age will be sent a urine pregnancy test and report the result by verbal report over telemedicine or phone. Patients returning for prescreening labs and vital signs may have a serum pregnancy test performed, instead. If negative, they will be considered eligible. Given the class D pregnancy class, women of childbearing age must be taking a study-allowed form of contraception for the study period. Patients will have potassium and creatinine screening to decrease the risk of both kidney injury and decreased clearance. Patients on dialysis or with an eGFR <30 will be excluded, and 30-60 will have half-dosing. Patients with a documented potassium >5.0 will be excluded. Patients with hypotension will be excluded given an expected decrease of 6-8 mmHg in their blood pressure. Finally, all patients or their legally authorized representative will provide prospective written informed consent.

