5.4 *Patient follow-up:* Participants will receive phone calls by trained study personnel every other day for the 10 days of the intervention period to monitor for the development of complications including lowest daily blood pressure (measured at least once by home blood pressure cuff provided to the patient and medication compliance. Data will be documented into a Redcap database. The coordinators will have participants complete 2 qualitative surveys at enrollment, day 4, and day 10 (both attached in supplement). Surveys and adverse event assessments conducted within 1 day of the time point will be counted as qualifying and not considered missing. At day 15 (+/- 2 day), patients will be asked to return for repeat research blood draw to include creatinine testing. Patients will be contacted by phone at day 28 (+/- 3 days) and 90 (+/- 3 days) for short and intermediate term outcomes. If there is no follow-up due to lack of patient response, this will be documented and not counted as a protocol deviation.

MEDICAL PROTOCOL (HRP-590)

SHORT PROTOCOL TITLE: Randomized control trial of losartan for outpatients with COVID-19

VERSION DATE:5APR2020

5.5 *Table of events:*

		Study Day																			
	Screening / Enrollment ^{t*}	1	2	3	4	5	6	7	8	9	10	11	12	13	14	15	28	90			
ELIGIBILITY																					
Covid-19 Result confirmation	X																				
Inclusion / Exclusion	X																				
Informed Consent	X																				
ADDITIONAL POST-ENROLLMENT PRESCREENING (IF NOT ALREADY AVAILABLE)																					
Pregnancy assessment and birth control X plan**	X																				
Blood Pressure within 1 week of randomization	X																				
Creatinine / Potassium within 1 week of randomization	X																				
Randomize subject if eligible after additional prescreening	X																				
POST-RANDOMIZATION																					
Demographics	X																				
Medical History / CRF	X																				
Dispense / administer study drug**	X	X	X	X	X	X	X	X	X	X	X										
STUDY PROCEDURES (while outpatient) #																					
Assessment of Hospitalization			X		X		X		X		X								X	X	
Adverse event assessment			X		X		X		X		X								X	X	
Review adherence			X		X		X		X		X										
Review and record blood pressures and temperatures			X		X		X		X		X										
PROMIS Survey					X							X							X		

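### Entry potassium and creatinine windows differ between 8.3, 5.2 and 5.5, and only one row of table 5.5 stops a patient with an old potassium (minor)

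*Combined protocol and SAP*

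**What the plan says.** Three places in the combined protocol and SAP set an age limit for the entry labs.

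- **Section 8.3 (exclusion criteria).** Potassium: "Potassium >5.0 mmol/L (must have been measured within 1 month) of enrollment". The eGFR criterion has the same length and anchor: "must be have been measured within 1 month of enrollment".
- **Section 5.2 (enrollment).** Patients who "do not have a documented creatinine and blood pressure reading within 7 days of the return of their positive COVID19 test results" are consented and enrolled, but must attend a screening visit before randomization. At that visit, "The additional screening procedures will include: a blood pressure, creatinine, and potassium".
- **Section 5.5 (table of events).** One row reads "Creatinine / Potassium within 1 week of randomization". It stands under the heading "ADDITIONAL POST-ENROLLMENT PRESCREENING (IF NOT ALREADY AVAILABLE".

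Two other places bear on the point without giving a window. Section 8.4 states the purpose: "Patients will have potassium and creatinine screening to decrease the risk of both kidney injury and decreased clearance". Section 6.2 says: "Baseline clinical laboratory results will be required to establish inclusion and exclusion criteria, and missing data will be reported as protocol deviations". It does not say how old a result may be before it counts as missing.

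**The concern.** The rules differ in length, in the date they count from (enrollment, return of the positive result, randomization) and in the tests they cover. Nothing ranks them. A coordinator working from the eligibility list and the visit trigger would find no reason to repeat a potassium that is several weeks old. A coordinator working from the table would repeat it.

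The entry potassium matters because it stands alone. Under 5.4, contact during the 10 dosing days is by phone and covers blood pressure, adherence and complications. The return blood draw is at day 15 (± 2 days), after dosing has ended. No potassium is scheduled between entry and that draw. Section 13.1 lists worsening renal function and electrolyte abnormalities among the most severe risks of losartan. The exclusions for kidney disease, dehydration with low urine output, low systolic pressure, current ACE inhibitor or ARB use, and aliskiren lower the risk, but none of them measures current potassium.

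**Working it through.** The plan states no derived figure to reproduce. The check compares the windows and follows one patient through them.

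**Inputs and assumptions**
- One month (8.3) is taken as 30 days. Using 28 to 31 days moves the 8.3 figures by −2 to +1 day.
- Randomization is within 72 hours of the test result (1.5) and of meeting inclusion criteria (8.3), so the gap *g* from enrollment to randomization is taken as 0 to 3 days.
- The 7 days in 5.2 are read as 7 days before the positive result, and lack of either creatinine or blood pressure is read as triggering the visit.
- The 1 week in 5.5 is 7 days before randomization.

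**Oldest result each rule lets through, in days before randomization**

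| Rule | Creatinine | Potassium |
|---|---|---|
| 8.3 alone | 30 + *g* = 30 to 33 | 30 + *g* = 30 to 33 |
| 5.2 trigger alone | 7 + 3 = 10 | not mentioned, so no limit |
| 5.5 row | 7 | 7 |
| All applied together | 7 | 7 |

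**Potassium.** Take a patient with creatinine and blood pressure recorded 3 days before the positive result, an acceptable eGFR, and a potassium of 4.8 mmol/L measured 28 days before enrollment.
1. 8.3: 28 days is within one month and 4.8 is not above 5.0. The patient passes.
2. 5.2: creatinine and blood pressure are both within 7 days of the result. No visit is triggered, so potassium is not repeated.
3. 5.5: creatinine and blood pressure are at most 3 + 3 = 6 days old at randomization, which meets 1 week. Potassium is 28 + 0 = 28 to 28 + 3 = 31 days old, which does not.

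Only step 3 stops this patient. The recent blood pressure is a necessary condition: without it, the 5.2 visit is triggered and potassium is drawn there.

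**Creatinine.** A sample drawn 7 days before the positive result, with randomization 1, 2 or 3 days after the result, is 7 + 1 = 8, 7 + 2 = 9 or 7 + 3 = 10 days old. It passes 8.3, does not trigger 5.2, and fails 5.5.

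**Effect of aligning the windows.** With all rules applied, the maximum age is 7 days before the change and 7 days after it: 7 − 7 = 0 days.

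**The case against.** The strongest reply is that these are successive conditions and not a conflict. Section 8.3 counts back from enrollment and table 5.5 from randomization, and both 5.2 and 5.5 place further screening between the two steps. A patient must meet every condition, so an old potassium can pass the first step and must be refreshed at the second. The table row names potassium and 1 week itself and does not depend on the 5.2 trigger. Its heading about results already available is most naturally read as meaning results within that week. The affected patient is also a narrow case, since 5.2, 5.5 and 8.4 all pair creatinine with potassium.

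Most of this stands. Read cumulatively, the protocol catches the patient, and two stronger inferences fail for that reason.

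- A reader might infer that the protocol permits month-old labs at randomization, so that the fix gains 30 − 7 = 23 to 33 − 7 = 26 days. That holds only against 8.3 read alone.
- A reader might infer that an old eGFR could put a patient on the wrong dose, since 4.1 gives 25 mg once daily at eGFR 30 to 60 and twice daily otherwise. An eGFR a month old could be used only by a site that disregarded both 5.2 and 5.5, so the plan does not allow it.

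What the reply does not remove is that the protocol never says the strictest window wins. The eligibility list accepts the old potassium in terms, and the trigger that decides who attends the screening visit omits the test. One table row is then the sole safeguard.

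**Conclusion.** The inconsistency is real and minor. It is a drafting fault with a safety consequence; nothing suggests that anyone chose to accept a month-old potassium. Two of the three rules let through a patient with recent creatinine and blood pressure and a potassium up to about a month old (30 to 33 days at randomization, on a 30-day month and a gap of 0 to 3 days). For creatinine, the live disagreement is limited to values aged 8 to 10 days, and rests on reading the 5.2 window as 7 days before the result plus the 72-hour limit.

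The permitted maximum under the protocol as a whole is unchanged at 7 days. What is at stake is whether sites apply the same rule, given that the next scheduled potassium comes after dosing. The documents do not allow an estimate of how many patients would be affected. Sample size, power and the primary comparison are untouched.

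**What to change.** Use the table 5.5 window in all three places.

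- **8.3:** change both the eGFR and the potassium windows to *within 1 week before randomization*.
- **5.2:** change the trigger to *creatinine, potassium or blood pressure not documented within 1 week before randomization*.
- **5.5:** no change needed.

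The cost is wording in two sections. Some patients will need the screening visit that 5.2 already provides and 5.5 already implies, and it must fit within the 72-hour randomization limit. No new procedure is added. The change does not guarantee a sample taken during the illness: with symptoms for 1 to 7 days at randomization, a 7-day-old result can still predate onset by 7 − 1 = 6 down to 7 − 7 = 0 days. The gain is one rule that every site can apply and a monitor can audit.
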